Version B	10 FEB 2017	Changed Painful Peripheral Diabetic Neuropathy to Diabetic Peripheral Neuropathy to allow for a broad symptomatology to be included. Added information to how many times VPT test will be conducted to obtain the average value at each time point. Added additional primary endpoint to capture changes in both large and small nerve fiber responses. Updated response assessment from VPT change to change in 1-point decrease in NPRS over the last 24 hours. Added additional instruction and a visual for collecting the foot measurement, updated introduction and background section, and added additional medications to "allowed medications" section. Removed EQ-5D questionnaire and replaced with Neuro-QoL questionnaires.
Version C	22 FEB 2017	Change testing of plantar aspect to dorsal aspect for QST heat and cold testing. Updated Exclusion #3 added a timeframe of within 6 months of the Screening Visit and an upper limit of 1.4 for the ABI.
Version D	27 MAR 2017	Removed Summary of Diabetes Self Care Activities Questionnaire (SDSCA) to reduce patient fatigue with answering questionnaires. Switched NeuroQoL questionnaire with a single neuropathy-and foot ulcer-specific quality of life instrument.
Version E	19MAY2017	Updated locations for biopsies to be taken as well as the central lab used in analyzing the samples.
Version F	12JUN2017	Increase the number of sites from 2 to 4. Update Inclusion/Exclusion criteria to allow for a broader population to be enrolled. Allow all patients to voluntarily consent to biopsies.

Study Title Protocol Number Name of Study Device Phase of Development Objective	AMulti-Center,Sham-Controlled,Double-BlindRandomized Withdrawal Study of Pulsed ElectromagneticField (PEMF) Therapy to Evaluate Vibration PerceptionThreshold and Thermal Sensory in Subjects with DiabeticPeripheral Neuropathy in the Lower ExtremityRBI.2017.001PROVANT® Therapy SystemProof of ConceptTo demonstrate the effectiveness of PEMF treatment compared
	to sham treatment in changing Vibration Perception Threshold (VPT) and Thermal Sensory (QST) in patients with diabetic peripheral neuropathy (DPN) when treatment is administered twice daily through 120-day period.
Number of Subjects	Up to 40 subjects randomized 1:1.

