Endpoints	For this proof of concept study, the primary endpoints will be changes in Vibration Perception Threshold and Quantitative Sensory Testing between baseline and end of treatment. Secondary endpoints will be changes in nerve conduction velocity (NCV) of the sural nerve and amplitude from baseline to end of treatment, changes in Skin Perfusion Pressure (SPP) from baseline to end of treatment, change in Pain Intensity using the 11-point Numeric Pain Rating Scale (NPRS) from baseline to end of treatment, change from baseline in Brief Pain Inventory (BPI) and Brief Fatigue Inventory (BFI), change from baseline in Patient Global Impression of Change (PGIC), change from baseline in Hospital Anxiety and Depression Scale (HADS), and changes from baseline in neuropathy and foot ulcer specific quality of life instrument (NeuroQoL).
	Safety will be assessed through review of Adverse Event (AE) reports and concomitant treatments and medications. All concomitant drug or non-drug treatments used during the study will be recorded. Safety outcomes will be assessed at the interim visits and the end of study visit.
Study Procedures	Following informed consent and assessment of eligibility, subjects will complete Section A-History of the Michigan Neuropathy Screening Instrument (MNSI) with Section B- Physical Assessment completed by the site. A measurement of the depth of the right foot will be measured from the most inferior aspect of the medial malleolus to the plantar aspect of the foot when residing on the treatment pad. The depth should not be more than 8cm for eligibility. A finger stick will be performed on the subject to obtain a baseline HbA1c value (A1C Now [®] test kit) and subjects will complete a Urine Drug Screen in office. Subjects will undergo the Ankle-Brachial Index (ABI), Venous Insufficiency Assessment, and Pain Phase evaluation (at least 10 subjects in each of the 2, 3, and 4 pain phases will be enrolled). For subjects of child bearing potential a urine pregnancy test will be obtained.

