Adverse events will be mapped to preferred terms and body systems using the Medical Dictionary for Regulatory Activities (MedDRA) coding dictionary. While the primary presentation of adverse events will be subject-based, the number of adverse events will also be reported. The number and percentage of subjects reporting each event will be summarized during the treatment period by treatment assignment. Incidence of adverse events by maximum reported severity will also be tabulated. Serious adverse events and adverse events leading to discontinuation will be displayed.

D. Eligibility Criteria

Eligibility for participation in this study will be based on the inclusion/exclusion criteria. An individual subject may only be included in the study once.

1. Inclusion Criteria

- 1. Subject age is greater than or equal to 22 years and less than 80 years of age.
- 2. Subject has documented Type 1 or Type 2 diabetes mellitus (receiving insulin, diet controlled, or taking parenteral hypoglycemic agents)
- 3. Subject is on a stable antidiabetic regimen (medication and/or diet) to control their diabetes for at least 30 days prior to Screening.
- 4. Subject has an HbA1c <10% at Screening or within 2 months of Screening.
- 5. Subject has daily pain attributed to bilateral symmetrical Diabetic Peripheral Neuropathy with numbness, tingling, and/or burning based on clinical judgement for at least 6 months prior to screening.
- 6. Subject's pain or discomfort from DPN is identifiable.

- 7. Subject is in pain Phase 2, 3, or 4 as per the Phasing of Neuropathy Scale.
- Subjects average pain over the last 24 hours is ≥3 based on the 11-point Numeric Pain Rating Scale (NPRS) at the Screening Visit.
- 9. Subject has adequate lower extremity pulse in both feet and no intermittent claudication.
- 10. Subject is able to ambulate independently with assistive devices, but not wheel chair bound.
- 11. Subject is willing and able to give written informed consent and to comply with all parts of the study protocol.
- 12. Female subjects must be post-menopausal, surgically sterile, abstinent, or practicing (or agrees to practice) an effective method of birth control if they are sexually active for the duration of the study (Effective methods of birth control include prescription hormonal contraceptives, intrauterine devices, double-barrier methods, and/or male partner sterilization).

2. Exclusion Criteria

- 1. Subject is in pain Phase 1 or 5 as per the Phasing of Neuropathy Scale.

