At the start of this study, all subjects will receive active devices. At Day 61, Day 75, or Day 91, if the subject becomes a responder based on a 1-point decrease in the average pain score using the Numeric Pain Rating Scale, the subject will be randomized 1:1 (active: sham). The sham devices will be PEMF devices that are de-activated such that no radiofrequency energy is generated or delivered when the device is started. All other functions, including the start sequence, display lights, audible start-beep and fan operation of the sham devices are identical to that of the active PEMF devices. Sham devices are indistinguishable from the active PEMF devices being used in the study. The subjects, research personnel at the investigative site, and sponsor will be fully blinded to the randomization assignment and unable to differentiate active and sham devices.

L. Study Assessments

All efficacy outcome measures will be assessed in order to allow for characterization of the response to PEMF therapy. All efficacy assessments will be conducted at the Enrollment Visit (Baseline; Day 0) and at the end of study visit (Day 121).

1. Primary Efficacy Assessments

Vibratory Perception Threshold (VPT): For large nerve fiber assessment. VPT is a non-invasive test used in quantifying sensation/sensitivity to vibration in evaluating sensory dysfunction associated with diabetic neuropathy. The hand-held vibratory stimulator will be placed against the midpoint of the plantar aspect and big toe of the right foot; the tester will initiate the automated test that will last between 5-10 minutes. Three tests will run at each location and the average of the 3 will be populated by the system. The VPT will be collected using the VSA-3000 Vibratory Sensory Analyzer at the midpoint on the plantar aspect and on the big toe of the right foot. VPT will be collected at the Enrollment Visit to obtain a baseline value and on Days 15, 30, 45, 61, 75, 91, 105 and 121.

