Randomization of subjects can occur at different times, depending on when the subject is determined to be a responder. Once a subject is determined to be a responder (based upon a 1-point decrease in average pain score over the last 24 hours using the NPRS), the subject will return the active devices and be randomized 1:1 to receive active treatment or inactive sham devices and be instructed to treat through study day 120. If a subject is determined to not be a responder at Day 91, i.e., their final chance to be randomized, the subject will be terminated from the study at the end of the Day 91 visit.

C. Summarization of Results

The tabulations will be based on the paired results for the change from the baseline to study day 120 for patients who are randomized, and separately for the last observation. Supportive subject data listings will be sorted and presented by subject number, visit date and relative study day. Listings will also include the number of days relative to the initiation of treatment. Two sets of analyses will be generated; summary tabulations for all randomized subjects who complete the baseline and study day 120 evaluations (*Completers Analysis Set*), and all randomized subjects using the baseline and last recorded set of evaluations (*End of Study Evaluation Set*). This latter set should include all subjects who were randomized and complete at least one set of evaluations after randomization.

Specific algorithms will be described in the Statistical Analysis Plan for imputing missing or partially missing dates, if deemed appropriate, under specific data topics. Imputed or derived data will be flagged in the individual subject data listings. Imputed data will not be incorporated into any raw or primary datasets. The imputed data will be retained in the derived / analysis datasets.

The total duration for a subject *on-study* will be calculated as the difference between the date of initial study treatment in the *Induction Phase* and the last day of observation plus 1 day. All calculations for defining the duration on-study will follow the algorithm DURATION = [STUDY COMPLETION OR WITHDRAW DATE – INITIAL TREATMENT DATE + 1].

Summary statistics will consist of the count and percentage in each level for categorical variables, and the sample size (n) mean, median, standard deviation (SD), minimum, and maximum values for continuous variables. All mean and median values will be formatted to one more decimal place

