than the measured value. Standard deviation values will be formatted to two more decimal places than the measured value. Minimum and maximum values will be presented with the same number of decimal places as the measured value. The number and percentage of responses will be presented in the form XX (XX.X%). Pairwise differences between the treatment groups will be calculated and 95% confidence intervals constructed.

While no formal hypothesis testing is planned, probability values may be generated to determine the magnitude of the difference between subject groups for an endpoint. All p-values that round to 0.0000 will be presented as '<0.0001' and p-values that round to 1.0000 will be presented as '>0.9999'. P-values <0.05 will be discussed as being statistically significant.

All summary tables will include the analysis population sample size (i.e., number of subjects). Study Day 1 is defined as the day the subject receives their initial exposure to the active study device. All *study days* are determined relative to the day of initial treatment with the study device. Baseline values will be defined as those values recorded closest to, but prior to, the first active study treatment during the initial phase of the study. Date variables will be formatted as DDMMMYYYY for presentation. Where appropriate, only the measurements from the right foot will be used in the calculations.

D. Adverse Events

All summaries of adverse events will be based on treatment-emergent adverse events. Adverse events will be provided in a listing. The number and percentage of subjects experiencing adverse events will be summarized. Summaries by maximum severity and relationship to the study device (active or sham) will also be provided. Serious adverse events and adverse events leading to discontinuation from the study will be presented. Treatment-related adverse events will be defined as adverse events with investigator assessment of related or possibly related. In summaries of adverse events by severity and relationship to study device, patients reporting multiple episodes will be counted once under the worst severity and the strongest relationship, respectively. Serious adverse events will also be presented by relationship to treatment. The number of patients with at least one adverse event will be tabulated for each treatment group. The number of adverse events for each treatment group will also be tabulated.

E. Sample Size

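### Randomisation is enriched on pain response only while VPT and QST are primary, and Section VI.C never uses the VPT/QST values taken at the randomisation visit

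*Combined protocol and SAP*

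**What the plan says.** The trial is an enriched-enrolment randomised withdrawal study (Section III.A). All subjects start on active devices. Section VI.B then sets the gate to randomisation: "Once a subject is determined to be a responder (based upon a 1-point decrease in average pain score over the last 24 hours", on the NPRS, judged at Day 61, 75 or 91. Neither VPT nor QST enters that gate. Nor do they enter eligibility, where the only threshold of this kind is on pain: "Subjects average pain over the last 24 hours is ≥3 based on the 11-point Numeric Pain Rating Scale (NPRS) at the Screening Visit". Section III.F describes 1:1 permuted blocks and names no stratification factor.

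The aim is sensory. The synopsis objective compares PEMF "to sham treatment in changing Vibration Perception Threshold (VPT) and Thermal Sensory (QST) in patients with diabetic peripheral neuropathy", and under Endpoints "the primary endpoints will be changes in Vibration Perception Threshold and Quantitative Sensory Testing between baseline and end of treatment". Pain is secondary: "change in Pain Intensity using the 11-point Numeric Pain Rating Scale (NPRS) from baseline to end of treatment".

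Section III.L.1 schedules VPT at two sites (plantar midpoint and big toe) with a "baseline value and on Days 15, 30, 45, 61, 75, 91, 105 and 121". QST (cold and heat) follows the same days. Every possible randomisation visit therefore has a VPT and a QST measurement.

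Section VI.C analyses paired change from baseline in randomised subjects, in a Completers set and an End of Study Evaluation set. Baseline is the value closest to, but "prior to, the first active study treatment during the initial phase of the study". Active-sham differences with 95% confidence intervals are planned. No formal testing is planned, but p-values may be produced, and those below 0.05 will be discussed as significant. Section VI.E calls the sample of 40 one of convenience, without power.

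**The concern.** Enrichment sharpens a withdrawal comparison on the measure used to select subjects. Here selection is on pain and judgement is on vibration and thermal thresholds. The current text does not say why a 1-point pain response should pick out subjects whose thresholds improved. If the two responses are only loosely linked, some randomised subjects carry little sensory gain into the withdrawal phase, and stopping treatment has less to undo in them.

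The plan also discards information that would help. Each subject's sensory change during induction is known at the randomisation visit, yet Section VI.C does not use it as a covariate, as a table or in interpretation. At stake is the reading of a null result. A small VPT/QST difference could be taken to mean that a sensory benefit was not maintained by treatment, when part of the explanation may be that the randomised group was not selected for having one. The plan calls for between-arm intervals and comment on p-values, so readers will interpret this contrast despite the proof-of-concept label.

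**Working it through.** **No planned figure to reproduce.** The documents give no effect size, SD, power or correlation between pain and sensory change. Everything below is illustration under stated assumptions.

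**1. Share of pain responders without a sensory gain.** Assume pain change and sensory change are bivariate normal with correlation ρ, and 60% are pain responders. If a proportion g of enrolled subjects gain on the sensory measure, the share without a gain among responders is 1 − P(pain response and sensory gain)/0.60.

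| g | ρ = 0 | ρ = 0.3 | ρ = 0.5 | ρ = 0.7 |
|---|---|---|---|---|
| 0.3 | 70% | 63% | 59% | 54% |
| 0.5 | 50% | 42% | 37% | 30% |
| 0.7 | 30% | 23% | 18% | 12% |

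The range is 12% to 70%. The documents do not locate the trial within it.

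**2. Effect on the contrast.** Let q be the share with a gain, δ the active-sham difference among them, and h the difference among the rest. The all-randomised contrast is qδ + (1 − q)h. Take δ = 1 SD.

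- If h = 0, the contrast is 0.30 SD at q = 0.30 and 0.88 SD at q = 0.88.
- If active subjects without an earlier gain still improve after randomisation by an assumed h = 0.5 SD, it is 0.30 + 0.70 × 0.5 = 0.65 SD and 0.88 + 0.12 × 0.5 = 0.94 SD.

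The shrinkage therefore depends on both q and h, and neither is known.

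**3. Precision available.** The 95% half-width for a two-arm difference is t × √(2/n) SD.

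- With 40 randomised (synopsis, Number of Subjects), n = 20 per arm: 2.024 × √(2/20) = 0.64 SD.
- With 40 enrolled (synopsis, Study Sample) and an assumed 70% response, 28 are randomised, n = 14: 2.056 × √(2/14) = 0.78 SD.
- At an assumed 60% response, 24 are randomised, or 12 per arm, and the interval is wider still.

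**4. What the pre-induction baseline does.** For each subject,

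change (Day 0 to end) = gain (Day 0 to randomisation visit) + change (randomisation visit to end).

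The first term arises before randomisation, on active devices in everyone. Its expected arm difference is zero, so it adds noise and chance imbalance but no treatment signal. The standard error of that imbalance is √(2/20) = 0.32 SD of the gain at 20 per arm and √(2/14) = 0.38 SD at 14.

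**5. What adjustment offers.** If the randomisation-visit information has correlation R with the outcome within arm, adjustment multiplies the standard error by about √(1 − R²).

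- R = 0.5: √0.75 = 0.87, a 13% cut.
- R = 0.6: √0.64 = 0.80, a 20% cut.
- R = 0.66: √0.564 = 0.75, a 25% cut.

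An illustrative simulation gave cuts of about 20% to 25%. At 20 per arm that takes the half-width from 0.64 SD to 0.64 × 0.80 = 0.51 SD or 0.64 × 0.75 = 0.48 SD. The real R is unknown. A lower R gives less, and at R near zero the cost is two degrees of freedom.

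**The case against.** **Post-randomisation gain.** Subjects kept on active devices treat for roughly 30 to 60 more days, and the objective speaks of treatment through 120 days. A reader might infer that active and sham can only differ in subjects who had already gained. The documents do not support that: a later gain on active treatment would also separate the arms. This stands, and it is why h appears in the working.

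**Size.** A reader might infer that most randomised subjects have no sensory gain. Nothing in the documents shows this; the share without a gain could be well under half. This also stands.

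**Purpose and status.** The study is a proof of concept with a convenience sample. It aims to explore mechanisms of increased sensation and pain relief, so studying sensation in pain responders can be a sensible choice. The comparison is unbiased for that population. The amendment log records that response was once judged on VPT change; that is superseded history and not evidence of error.

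**A separate SAP.** Section VI says the detail sits in a separate SAP, which is not among the material supplied, so it may already address this. But Section VI also calls itself the basis for that SAP, and it names no use of the randomisation-visit values.

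**Splitting by gain.** Restricting the comparison to subjects who improved during induction looks like the natural remedy. It is weaker than it looks: any value better than Day 0 counts as a gain, and under pure measurement noise about half of subjects with no true gain would pass. An arm-by-gain interaction would be very imprecise at 20 or fewer per arm. With two VPT sites, two QST modalities, two analyses and two analysis sets, such splits could add 2 × 2 × 2 × 2 = 16 results without a multiplicity plan. This stands, and it limits the remedy.

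**Conclusion.** The mismatch is explicit: selection is on NPRS alone, the primary endpoints are VPT and QST, and the planned analysis leaves out sensory values already measured at the point of randomisation. The consequence is a possible loss of sensitivity in the VPT/QST contrast. It is not bias, since the all-randomised comparison remains valid for pain responders, and no stated figure is contradicted.

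The size is unknown. The 12% to 70% without a sensory gain rests on an assumed 60% pain response, 30% to 70% sensory gain and correlations of 0 to 0.7. The benefit of adjustment, about 13% to 25% off the standard error for R between 0.5 and 0.66, is likewise conditional. A reader might conclude that the design cannot detect a sensory effect, or that it has a particular low power; the documents support neither. What does follow is that a null VPT/QST contrast would not by itself show that a sensory gain failed to be maintained.

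**What to change.** No change to who is randomised is proposed. In Section VI.C and the SAP:

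1. For each VPT site and each QST modality, prespecify a linear model in all randomised subjects of the end-of-study value (or change) on arm, adjusted for the Day 0 value and the value at the randomisation visit. Entering Day 0 and the induction gain instead gives the same arm estimate. Report it beside the planned unadjusted difference and 95% interval.
2. Tabulate VPT and QST change from Day 0 to the randomisation visit by arm.
3. State that enrichment was on pain, and that a null VPT/QST contrast is therefore not by itself evidence that a sensory gain was lost or not maintained.
4. Label any gain-subset or arm-by-gain interaction result as descriptive only.

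Both adjusting values precede the switch of devices, so the randomised comparison is preserved. The cost is SAP wording, one table, and four measures × two analysis sets = eight adjusted estimates. No new data are needed. Prespecification matters because the same adjustment chosen after unblinding would be open to the charge of selection.

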- Request for withdrawal by the subject for reasons other than an intolerable AE.
- Lost to follow-up, as determined by failure to respond to at least 2 telephone calls followed by certified letter sent to the subject's last known address. All attempts to contact the subject must be documented in the subject's source documents.

VI. STATISTICAL CONSIDERATIONS

The statistical analysis of the study is described in detail in a separate version-controlled prospective Statistical Analysis Plan (SAP). However, the statistical methodology described in this section of the protocol will be the basis for the detailed SAP.

This bi-phasic design includes 2 sequential periods: the *Induction Phase* and *Randomized Withdraw Phase*. All safety analyses will be performed on the *Safety Analysis Set*, defined as all subjects who were enrolled into the study and issued study devices during the *Induction Phase* and followed through the *Randomization Withdraw Phase* or until they withdraw. Once a subject is determined to be eligible, the subject will be issued active treatment devices and the subject will be formally enrolled into the study and become part of the *Safety Analysis Set*. Where not otherwise specified, the last pre-treatment observation will be used as baseline for calculating post-treatment changes from baseline.

A. Induction Phase / Baseline Evaluations

Prior to study treatment, subjects will complete the baseline health economic questions, including the Brief Pain Inventory (BPI), Brief Fatigue Inventory (BFI), Hospital Anxiety and Depression Scale (HADS), and the NeuroQoL. Vibration Perception Threshold (VPT), Quantitative Sensory Test (QST) and Nerve Conduction Velocity (NCV) will be completed. Skin Perfusion Pressure

(SPP) will be performed to obtain a baseline value of the plantar and dorsal aspect of the right foot. Once the subject is determined to be eligible, the subject will be issued active treatment devices and the subject will be formally enrolled into the study and become part of the *Safety Analysis Set*.

Subjects in the *Safety Analysis Set* will be instructed in the use of the devices for 60 days in the home environment. At Days 15 and 45, subjects will return to the clinic to have the VPT and QST conducted. Subjects will return to the clinic at days 30 and 61 for evaluation and complete questionnaires.

B. Randomized Withdraw Phase

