This is a proof of concept study with no formal hypothesis testing planned and therefore there is no power associated with this study. The sample size of 40 patients is a sample of convenience for this study.

VII. INFORMED CONSENT

It is the responsibility of the investigator, or a person designated by the investigator (if acceptable by local regulations), to obtain written informed consent from each individual participating in this study after adequate explanation of the aims, methods, objectives and potential hazards of the study. It must also be explained to the subjects that they are completely free to refuse to enter the study or

to withdraw from it at any time for any reason. Appropriate IRB-approved forms for obtaining written informed consent will be provided by the investigator or by Regenesis Biomedical, Inc. or their designee.

If new safety information results in significant changes in the risk/benefit assessment, the consent form will be reviewed and updated if necessary. All subjects (including those already being treated) will be informed of the new information, given a copy of the revised form and be re-consented to continue in the study.

VIII. INSTITUTIONAL REVIEW BOARD

This protocol, the informed consent form and any accompanying material provided to the subject (such as subject information sheets or descriptions of the study used to obtain informed consent) as well as any advertising or compensation given to the subject, will be submitted by the investigator or investigator's designee to an IRB. Approval from the IRB must be obtained before starting the study and should be documented in a letter to the investigator specifying the date on which the IRB met and granted the approval.

IX. TERMINATION OF THE INVESTIGATION

As the study sponsor, Regenesis Biomedical, Inc. reserves the right to terminate the study at any time. Should early termination be necessary, Regenesis Biomedical, Inc. and the investigator will consult and make sure that adequate consideration is given to the protection of subjects' interests.

Additionally, all clinical investigational data will be reviewed by the sponsor on a regular basis. Reports of all data will be made available to the Institutional Review Boards and to the FDA as required. Unanticipated adverse device events will be evaluated and reported in accordance with 21 CFR Part 812 requirements and as required by the governing IRB.

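### Section VI.C disclaims hypothesis testing but requires any p-value below 0.05 to be discussed as statistically significant, and treats p-values as a measure of effect size

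*Combined protocol and SAP*

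**What the plan says.** Three statements stand close together in Section VI.C (Summarization of Results):

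- Estimation: "Pairwise differences between the treatment groups will be calculated and 95% confidence intervals constructed".
- Status and purpose of p-values: "While no formal hypothesis testing is planned, probability values may be generated to determine the magnitude of the difference between subject groups for an endpoint".
- Labelling rule: "P-values <0.05 will be discussed as being statistically significant".

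Section VI.E (Sample Size) repeats that there is "no formal hypothesis testing planned and therefore there is no power associated with this study" and adds: "The sample size of 40 patients is a sample of convenience for this study".

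The introduction to Section VI refers to a separate SAP, which is not among the documents, and says that "the statistical methodology described in this section of the protocol will be the basis for the detailed SAP".

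In the synopsis (Endpoints), "the primary endpoints will be changes in Vibration Perception Threshold and Quantitative Sensory Testing between baseline and end of treatment"; the secondary endpoints follow. VI.C plans summaries in two overlapping sets, the Completers Analysis Set and the End of Study Evaluation Set.

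The protocol names no test, no sidedness, no single lead measure and no multiplicity adjustment. It does not describe p-values as nominal or descriptive.

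**The concern.** There are two faults of wording.

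1. Calling a result statistically significant because it falls below a fixed 0.05 cut-off is the decision step of a hypothesis test. A plan that disclaims testing and power cannot consistently prescribe that verdict. The rule is also unrestricted: it covers any endpoint and either analysis set.

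2. VI.C gives p-values the job of showing how large a difference is. A p-value mixes the size of the effect with the sample size and variability, so it cannot do that job. The differences and confidence intervals planned in the preceding sentence can.

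What is at stake is the reading of the results. If p-values are produced, a chance finding in a small unpowered sample must be given a label that readers could take as confirmation that the device works. The absence of family-wise error control is not itself the fault, since an exploratory study does not need it.

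**Working it through.** **There is no plan figure to reproduce.** The 40 subjects rest on no effect size, SD or power. The check is therefore a reading of the text, followed by two calculations of its consequences.

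**Step 1: what the rule binds.** Producing p-values is optional in VI.C; discussing those below 0.05 as significant is not. Nothing in Section VI limits the rule or softens the label.

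**Step 2: how many comparisons it could reach.**

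| Count | Primary | Secondary | Total |
|---|---|---|---|
| As named in the synopsis | 2 (VPT, QST) | 9 (NCV, sural amplitude, SPP, NPRS, BPI, BFI, PGIC, HADS, NeuroQoL) | 11 |
| Split by site and modality (Section III.L) | 4 (VPT at plantar midpoint and big toe; QST heat and cold) | 10 (SPP dorsal and plantar) | 14 |

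The split count is derived; the protocol does not state it.

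**Step 3: chance of at least one label when there is no effect.**

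Assumptions: each of k p-values is two-sided and produced in one analysis set, and the test statistics are standard normal with a common correlation ρ. The documents give no correlations, so ρ runs from 0 to 0.7.

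- At ρ = 0, device-favouring: 1 − 0.975^k. For k = 2, 1 − 0.975² = 0.0494.
- At ρ = 0, either direction: 1 − 0.95^k. For k = 2, 1 − 0.95² = 0.0975.
- At ρ > 0, device-favouring: 1 − ∫ Φ((1.96 − √ρ·u)/√(1−ρ))^k φ(u) du, integrated numerically. The two-sided version uses the probability of lying between −1.96 and 1.96.

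| k | Direction | ρ = 0 | 0.3 | 0.5 | 0.7 |
|---|---|---|---|---|---|
| 2 | device-favouring | 0.0494 | 0.0476 | 0.0454 | 0.0417 |
| 2 | either | 0.0975 | 0.0951 | 0.0907 | 0.0835 |
| 4 | device-favouring | 0.0963 | 0.0874 | 0.0779 | 0.0652 |
| 4 | either | 0.1855 | 0.1740 | 0.1558 | 0.1304 |
| 11 | device-favouring | 0.2431 | 0.1907 | 0.1520 | 0.1115 |
| 11 | either | 0.4312 | 0.3748 | 0.3036 | 0.2229 |
| 14 | device-favouring | 0.2984 | 0.2243 | 0.1744 | 0.1244 |
| 14 | either | 0.5123 | 0.4383 | 0.3480 | 0.2488 |

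Simulated two-sample t-tests (45,000 draws, 10 and 20 per arm, ρ of 0 and 0.7) agreed within 1.1 percentage points. No figure is given for the two analysis sets together, because VI.C plans summaries in both but does not say that p-values will be produced in both.

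**Step 4: why p does not measure magnitude.** For a two-sided equal-variance t-test with n per arm, p = 0.05 corresponds to an observed difference, in SD units, of t(0.975, 2n−2) × √(2/n):

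| n per arm | t | √(2/n) | Difference at p = 0.05 |
|---|---|---|---|
| 20 | 2.024 | 0.3162 | 0.64 SD |
| 10 | 2.101 | 0.4472 | 0.94 SD |
| 5 | 2.306 | 0.6325 | 1.46 SD |

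Twenty per arm means that all 40 subjects are randomized 1:1. The 10 and 5 per arm are assumed, since only responders are randomized and no expected number is given. Conversely, a fixed difference of 0.6 SD gives p = 0.065 with 20 per arm and p = 0.196 with 10.

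**The case against.** The best defence is that this is reporting language in a study plainly framed as proof of concept. P-values may never be produced. The label is the conventional name for p < 0.05 and does not mean confirmed. With a matching test, a 95% interval that excludes zero carries the same information and is equally unadjusted. For the two named primary endpoints the device-favouring chance is below 5%. The unseen SAP may already call p-values nominal.

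Much of this limits the size of the point. The consequence is conditional on p-values being produced, and the larger rates need all of them. The design, data and estimates do not change.

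The rates also depend on choices that the protocol leaves open:

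- **Sidedness.** If the 0.05 were one-sided, the device-favouring ranges would rise to about 8.0–9.8% (k = 2), 12–18.5% (k = 4), 19–43% (k = 11) and 21–51% (k = 14).
- **Counting.** Taking NCV and amplitude as one endpoint gives 10 named items, and 40% instead of 43% in either direction at zero correlation.
- **Model.** One common correlation across nerve, perfusion, mood and global-impression measures is a crude description.

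None of this removes the contradiction. The rule prescribes the verdict of a test that the plan disclaims, no text qualifies it, and Section VI is declared the basis for the SAP, so the rule carries forward by default. The equivalence with confidence intervals is a reason to describe the intervals as unadjusted too, which the fix does. The magnitude wording is wrong on any reading.

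**Conclusion.** The concern holds as stated, with high confidence as to the protocol text; how the SAP treats p-values cannot be checked. VI.C contradicts itself and VI.E by disclaiming testing while requiring a significance label, and it misdescribes what a p-value measures.

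Under the assumptions in the working, a spurious device-favouring label has a chance of 4.2–4.9% over the two named primary endpoints and 11–24% over the 11 named items. For the derived counts it is 6.5–9.6% over four primary measures and 12–30% over 14. In either direction the four ranges are 8.4–9.8%, 22–43%, 13–18.5% and 25–51%.

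This should be corrected because it governs what the report may claim. It does not affect trial conduct.

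**What to change.** In Section VI.C:

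1. Delete the sentence "P-values <0.05 will be discussed as being statistically significant".
2. In the sentence before the p-value formatting rules, remove the stated purpose of determining magnitude. Say instead that any p-values are nominal, unadjusted for multiplicity and descriptive.
3. Add a sentence that interpretation rests on the planned treatment differences with 95% confidence intervals. It should say that these are also unadjusted, so an interval excluding zero is an exploratory finding and not multiplicity-controlled confirmation.

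Carry the same wording into the SAP.

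The cost is two changed sentences and one added, with no new data, subjects or procedures. A rule of interpretation is arguably not administrative, so Section IV.M would call for a short formal amendment. The sponsor also gives up calling any result statistically significant, which follows from having disclaimed formal testing.
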